The patients will be randomized with 1:1 ratio of intervention and control groups, in blinded blocks of 5, randomly assigned by software used on www.randomizer.org to create 60 study patients and 60 control patients. Envelopes will be used to assign the patients in blocks of 5. Therefore in the first group is to be a control group, the first 5 patients will be controls, then the next group of 5 will be randomly assigned to control or intervention group based on a randomized protocol listed on a study envelope. Overall the blocks of 5 will create even groups of control and intervention patients overall to reach the 120 patient goal. One member of the study team, not involved in the surgical procedure and post-operative pain evaluation will be designated unblended and will communicate with the anesthesiology team pre-operatively to determine whether the patient is to receive methadone or not. The anesthesia team will be responsible for allocation and administration of the methadone, in addition to the standard fentanyl and ketamine, from the Montefiore pharmacy which is already available for intra-operative use as an alternate narcotic regimen. Post-operatively, blinded team members will collect pain data, as well as time to ambulation and discharge data. The pain measures will be patient derived, and time to event data will be part of the patient's chart.

Describe what safety outcomes will be monitored

Safety outcomes to be measured as stated in the adverse events section of this protocol include risks of using any opioid narcotic, which include overdose leading to respiratory depression, dependence and QTc prolongation. Psychological risks include obtunded, lethargic state or altered mental status due to long half-life and opioid effects post-operatively and any resultant mental distress, especially in opioid-naïve patients

Include a data safety monitoring plan

A data safety monitoring plan is included in section 7, under the subheading "Describe methods for interim analyses or early stopping, if applicable"

➤ For Observational studies

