 We proposed to recruit 60 patients to undergo the new treatment and another 60 as controls. This gives us greater than 80% (95%) power to detect an improvement of 0.56 (0.74) within-group standard deviation at statistical significance level 0.05 as had been calculated to be 51 patients per group. Using 60 patients will ensure the usability of our data to detect differences of this effect sizes between groups. From our preliminary data, the standard deviation of time to discharge is 6.7 days, therefore, our sample size is able to detect an average reduction of 3.8 days (5.0 days) in time to discharge with 80% (95%) power.

Describe methods for interim analyses or early stopping, if applicable A data safety monitoring committee will be organized for the purposes of data evaluation in this study.

The members of the committee will include [name], neurosurgeon in the Department of Neurosurgery who performs spinal surgeries yet is not involved in the implementation of this project, and [name], statistician in the Department of Epidemiology and Population Health who is not involved in this protocol. After 20 patients complete the study (approximately 10 patients in each arm), interim analyses will be performed to compare pain ratings, narcotic usage, time to ambulation, and time to discharge to control patients, and the data safety monitoring committee will be asked to review all results and advise the study personnel as well as the IRB about study continuation. If there a significant increase in any of these measured values beyond a single standard deviation of the mean, the data safety monitoring committee and the IRB will come to a decision regarding continuation of the study. Assuming the outcome follows a normal distribution, with 10 patients in each arm, and under the null hypothesis that there is no difference between two groups, the chance of observing a difference greater than or equal to one standard deviation between two groups is about 1/100000. With four measures considered here, the overall Type I error will be no greater than 5/100000. Therefore, the loss of power from the

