interim analysis is negligible. If the methadone intervention contributes greater than normal adverse events (>2 patients) the study will be held from further recruitment. The study medication will not be administered further, no dosing changes will be made, and the IRB will be informed. A decision at this point will be reached regarding further accrual. If a patient should die prior to discharge, a thorough cause analysis will be implemented by the DSMB, the IRB, in addition to the analysis that will already be performed by the hospital. If it is due to the surgery outside of the trial mediation, the data for this patient will not be used and the information will be explicitly reported in any publication yet kept separated from the other patient's data, as it would not be feasible or make sense to include this patient in the analysis. If this adverse event is found to be caused by the methadone administration, the trial will be stopped. This is however an extremely unlikely scenario as methadone is used daily by millions of individuals, has already been approved by the FDA, and our study patients will undergo a rigorous screening, namely for QTc prolongation, to remove any potential risk of death as a result of methadone administration. The only wayy to address this possibility is to have a plan to remove this patient's data from the other patient's data, with a clear note made in the report.

Describe how possible confounding and/or effect modification will be addressed. The possible confounders have been addressed via the strict inclusion and exclusion criteria of the study. Other confounding variables including past narcotic usage, and a cutoff of <10mg equivalents of morphine will be considered when selecting patients for participation in this study. Such a low daily morphine dose is unlikely to significantly impact methadone effect or post-operative narcotic use in patients with this low level of narcotic usage compared to narcotic-naïve patients. Patient time to ambulation will be confounded by baseline neurological status and therefore we will randomly assigning patients to each arm of the study as described above. Confounding in regards to time of operative procedure and complexity of surgery will be controlled properly with appropriate randomization.

Describe how loss to follow up will be addressed

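### The data safety committee's only scheduled review, after 20 patients, covers none of the safety outcomes the protocol names, and the adverse-event hold gives no one the task of counting events by arm

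*Combined protocol and SAP*

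**What the plan says.** Section 2, under the item on safety outcomes, lists the medical risks of opioids, "which include overdose leading to respiratory depression, dependence and QTc prolongation", and adds psychological risks: an obtunded or lethargic state and altered mental status. The next item says "A data safety monitoring plan is included in section 7", under the heading on interim analyses and early stopping.

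Under that heading, section 7 sets up a committee of a neurosurgeon and a statistician, neither involved in the project. After 20 patients complete the study, about 10 per arm, "interim analyses will be performed to compare pain ratings, narcotic usage, time to ambulation, and time to discharge to control patients". The committee reviews all results and advises the study personnel and the IRB on continuation. The trigger is a rise of more than one standard deviation in any of these measured values, which the protocol itself counts as four.

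Two further rules have no fixed date. If methadone contributes more adverse events than normal, in more than two patients, recruitment is held: "The study medication will not be administered further, no dosing changes will be made, and the IRB will be informed". A decision on further accrual follows, with no decision-maker named. If a patient dies before discharge, the DSMB and the IRB analyse the cause, and the trial stops if methadone is found responsible.

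On blinding, section 2 has one unblinded study member, not involved in surgery or post-operative pain evaluation, tell the anesthesia team the assignment. "Post-operatively, blinded team members will collect pain data, as well as time to ambulation and discharge data".

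**The concern.** The part of the protocol designated as the safety plan does not tell the committee to look at the protocol's own safety outcomes. A committee that followed section 7 to the letter could advise continuation after 20 patients without seeing a single respiratory or mental-status event by arm, and would not be asked again on any fixed date.

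The four reviewed measures are an imperfect stand-in for harm. Over-sedation could plausibly lower reported pain and narcotic use, which would look favourable, while lengthening time to ambulation and time to discharge, which would not.

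The adverse-event hold could fill the gap, but it turns on whether methadone is contributing more events than normal. That is a comparison between arms, or with a reference rate. The protocol gives no reference rate, does not say which events count, and gives nobody the task of tabulating events by arm.

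**Working it through.** **Planned totals.** The protocol's 51 per group reproduces: with two-sided alpha 0.05, 80% power and 0.56 SD, n = 2(1.960 + 0.842)²/0.56² = 50.1, rounded up to 51. It plans "to create 60 study patients and 60 control patients", 120 in all. These totals are not in dispute.

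**Safety outcomes set against the interim list.**

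| Named in section 2 | Compared at the section 7 review |
|---|---|
| Respiratory depression | No |
| Dependence | No |
| QTc prolongation | No |
| Obtunded, lethargic or altered mental state | No |

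The measures that are compared (pain, narcotic usage, time to ambulation, time to discharge) include none of the four.

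**Patients after the only scheduled review.** 120 − 20 = 100, and 100/120 = 83%. On methadone, using the protocol's approximate 10 at the review, 60 − 10 = 50, also 83%. That 50 is not guaranteed, because whole blocks of five go to one arm: "the first 5 patients will be controls, then the next group of 5 will be randomly assigned to control or intervention group". Taking 24 blocks, 12 of them methadone, the first four blocks contain m methadone blocks with probability C(12,m)·C(12,4−m)/C(24,4):

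| Methadone patients among first 20 | Probability | Methadone patients still to come |
|---|---|---|
| 0 | 4.7% | 60 |
| 5 | 24.8% | 55 |
| 10 | 41.0% | 50 |
| 15 | 24.8% | 45 |
| 20 | 4.7% | 40 |

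Since the review lists no safety outcome, the strict count of methadone patients without a scheduled committee review of the named harms is all 60.

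**What a look at 10 methadone patients could show, even with safety added.** The only over-sedation rates in the protocol are from the caesarean series in section 1: 1 of 25 on methadone (4%) and 3 of 50 controls (6%). That is a different population, so these are illustrations. P(no event in 10) = (1 − p)¹⁰: 0.96¹⁰ = 66% at 4%, and 0.88¹⁰ = 28% at an assumed 12%. A single early look is therefore weak.

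**What the hold rule could do.** P(at least 3 events in 60) = 1 − Σ C(60,k) pᵏ(1 − p)⁶⁰⁻ᵏ, k = 0 to 2, assuming independent events that are all recognised and counted:

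| Assumed rate | P(at least 3 in 60) |
|---|---|
| 2% | 12% |
| 4% | 43% |
| 6% (cited control rate) | 71% |
| 12% | 98% |

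At 12% the third event is expected near methadone patient 3/0.12 = 25. So a working hold would very probably catch a rate that high. But at the cited control rate, with no methadone excess at all, three or more events would still occur 71% of the time (1 − 0.024 − 0.094 − 0.176 = 0.706). A bare count cannot tell the two situations apart, so the rule needs events counted in both arms.

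**The case against.** The strongest reply is that harm is monitored throughout. The hold and the death analysis apply to every patient, the death analysis does involve the DSMB, and section 6 provides for nursing observation and naloxone. The committee is asked to review all results, which can be read to include adverse events. The trigger is an increase, the worse direction, so prolonged ambulation or discharge from over-sedation could reach it. And the hold rule's silence about the committee is not exclusion.

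Much of this stands. A reader might infer that there is no safety monitoring after patient 20; the documents do not support that. Nor do they support the inference that nobody who sees an event also knows the arm. The anesthesia team is told the assignment, gives the methadone and may see early respiratory events, and the unblinded member is kept from pain evaluation but not expressly from handling adverse events. It would also be wrong to read the 66% and 28% as the chance that harm goes unnoticed, because they leave out the hold.

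What the reply does not do is put the named harms before the committee on any schedule. The request to review all results closes the sentence that lists the four measures, and the trigger refers back to those alone. The death analysis does not reach non-fatal respiratory depression or altered mental status. The anesthesia team has the knowledge, but no counting or reporting role.

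**Conclusion.** The point holds as a gap in scheduled committee review, not as an absence of safety monitoring. The one scheduled review covers none of the named safety outcomes; 100 of 120 patients follow it; and on a strict reading all 60 methadone patients lack a scheduled committee review of those harms. The hold rule runs throughout, but names only the IRB, depends on an undefined normal rate, and leaves the count by arm unassigned.

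This rests on reading the interim list as complete, on treating the committee and the DSMB as the same body, and on the planned 1:1 totals. The event-rate figures are illustrations from a caesarean series and an assumed 12%; the conclusion does not depend on them. It is a cheap change that improves patient protection and is worth making.

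**What to change.** In section 7, at the interim review, add a table by arm of the section 2 safety outcomes that the chart records, plus all adverse events and deaths. State what the chart will supply for dependence and for QTc, since the only EKG the protocol mentions is pre-operative and the study ends at two weeks. Repeat this table at stated intervals during accrual, for example every 20 to 40 patients, with no efficacy comparison, so the added reviews spend no alpha.

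In the hold rule, send adverse-event reports from both arms to the committee statistician, who is given the allocation list and counts events by arm, so the clinical team stays blinded. Name the committee alongside the IRB as informed, and say who decides on further accrual. The sponsor should state what normal means and which events count; the threshold itself is for the sponsor.

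The cost is protocol wording, a few short tables from chart data, and a little time from a committee that already exists.

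### The interim rule's stated false-trigger probability (1/100000 per measure, 5/100000 over four) is too small by a factor of 1000 or more; on the plan's own assumptions it is about 1.3% per measure and up to about 5% overall.

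*Combined protocol and SAP*

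**What the plan says.** The interim plan is in section 7 (Data Analysis), under interim analyses and early stopping.

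- Timing: "After 20 patients complete the study (approximately 10 patients in each arm), interim analyses will be performed".
- Content: the analysis will "compare pain ratings, narcotic usage, time to ambulation, and time to discharge to control patients".
- Trigger: "If there a significant increase in any of these measured values beyond a single standard deviation of the mean", the committee and the IRB decide whether the study continues.
- Assumptions behind the probability: a normal outcome, 10 per arm and no true difference.
- Probability per measure: "the chance of observing a difference greater than or equal to one standard deviation between two groups is about 1/100000".
- Probability overall: "With four measures considered here, the overall Type I error will be no greater than 5/100000".
- Conclusion: the plan infers directly from these two figures that the loss of power from the "interim analysis is negligible".

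No formula is shown for either probability.

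**The concern.** With only 10 patients per arm, a difference in means of one SD is not a rare event under the null. It lies a little beyond the usual 5% two-sided limit. A probability of 1/100000 needs a Z of more than 4, and a one-SD difference between two groups of 10 cannot give that.

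These probabilities are the only operating characteristics stated for the rule, and they stand in the text on which the committee and the IRB will rely. A reader who accepts them would take a one-SD excess in any measure as near-proof of harm. In fact, if methadone has no effect, about one trial in 20 could reach a continuation decision by chance. The plan's statement about loss of power is also drawn from these figures alone, so it has no valid support as written.

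**Working it through.** **Inputs, all from the plan.** Section 7: normal outcome, 10 patients per arm, no true difference, threshold of one SD, four measures. Section 2 (randomization): "The patients will be randomized with 1:1 ratio of intervention and control groups". The power paragraph of section 7 expresses effects in within-group SDs, and the same unit is used here.

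**Standard error and Z.** For two independent means of n = 10,

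SE = SD × √(1/10 + 1/10) = 0.447 SD, so Z = 1/0.447 = 2.236.

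**Per measure.** One-sided, 1 − Φ(2.236) = 0.01267. Two-sided, 2 × 0.01267 = 0.02535. Against the stated 0.00001 these are 1267 and 2535 times larger. A simulation of 400,000 trials gave 0.0128 and 0.0253.

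**Over four measures.** The upper bound is four times the per-measure value. With independent measures the figure is 1 − (1 − p)⁴.

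| Reading | Per measure | Four measures, independent | Four measures, upper bound |
|---|---|---|---|
| One-sided, SD known | 1.27% | 4.97% | 5.07% |
| Two-sided, SD known | 2.53% | 9.76% | 10.14% |
| One-sided, SD estimated (t, 18 df) | 1.91% | 7.43% | 7.65% |
| Two-sided, SD estimated (t, 18 df) | 3.82% | 14.44% | 15.30% |
| Stated in the plan | 0.001% | – | 0.005% |

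The upper bounds exceed the stated 0.005% by factors from 5.07/0.005 = about 1010 to 15.30/0.005 = 3060. With positively correlated measures (one-sided, SD known, simulated), the overall figure is 4.6%, 4.2% and 3.1% at common correlations of 0.3, 0.5 and 0.8.

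**Can the plan's figure be reproduced?** Not with a valid two-sample calculation.

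- SE = SD/√10, as for one sample of 10: Z = 3.16, giving 0.0008 one-sided or 0.0016 two-sided. This is still about 80 to 160 times the stated value.
- SE = SD/√20: Z = 4.47, two-sided 0.0000077, and times four 0.000031. This fits both stated figures, but the standard error is half the correct size. It is a likely source of the error, not a proven one.
- Working backwards, a probability of 0.00001 at one SD needs n = 2Z² per arm: 2 × 4.265² = 36.4 one-sided, or 2 × 4.417² = 39.0 two-sided. At 10 per arm it needs a difference of 4.265 × 0.447 = 1.9 SD (one-sided).

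**Consistency with the plan's own sample size.** The power paragraph gives 51 per group for 0.56 SD at 80% power. The standard calculation gives 2 × (1.960 + 0.842)²/0.56² = 50.1, rounded up to 51. That formula uses SE = SD × √(2/n), which at n = 10 is the 0.447 SD above. The sample size therefore rests on the right standard error, and the interim figure does not agree with it.

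**Unequal split at the look.** Section 2 assigns whole blocks of five to one arm, so the first 20 patients are four blocks and need not split 10:10. At 5:15, SE = SD × √(1/5 + 1/15) = 0.516 SD, Z = 1.94, and the one-sided chance is 2.6% per measure.

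**Loss of power.** If methadone truly improves a measure by 0.56 SD, a worsening of at least one SD has probability 1 − Φ((1 + 0.56)/0.447) = 1 − Φ(3.49) = 0.00024, or 0.02% per measure.

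**The case against.** The strongest case on the other side concerns consequences. The trigger is an increase, all four measures are worse when higher, and crossing it leads to a decision rather than an automatic stop. The final significance level, the sample size and the main analysis are unchanged. If methadone has the benefit the trial is sized for, a false trigger is rare (0.02% per measure), so a small loss of power may well be true. The committee includes an independent statistician and reviews all results, so the plan does not imply that it would act on the printed probability alone. All of this stands. It limits the damage, but it does not make the stated probabilities right, and it supports the power statement by an argument that the plan does not make.

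A second objection is that 1.3% and 5% are not the only correct figures. This also stands. They assume a one-sided reading and a known SD, and the 5% is reached only if the measures are close to independent. Strong positive correlation lowers the overall figure to about 3%. A two-sided reading or an estimated SD raises it. No variant comes within two orders of magnitude of the plan's values.

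The trigger also asks that the increase be significant. That does not help: a one-SD difference at 10 per arm already has a two-sided P below 0.05 (0.025 with known SD, 0.038 with the t-test).

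**Conclusion.** The concern holds. On the plan's own assumptions, the chance of a false trigger is 1.3% per measure in the harmful direction (2.5% in either direction) and at most 5.1% (10.1%) over four measures. The plan states 0.001% and 0.005%. The per-measure understatement is about 1270-fold one-sided and 2530-fold two-sided with a known SD, and larger if the SD is estimated from the 20 patients. The overall figure is about 3% to 5% one-sided with known SD, depending on the correlation between measures.

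The error does not directly raise the final type I error, and the loss of power under the planned benefit is probably small. What fails is the stated behaviour of the rule on which continuation is decided, and the reasoning that leads from it to the power statement. This must be corrected before the committee uses the text.

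**What to change.** Replace the two probability sentences in section 7 with wording such as:

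> For normal outcomes with known SD and 10 patients per arm, the chance under the null that a measure is higher by at least one SD with methadone is about 1.3% (2.5% for a difference in either direction). Over four measures it is at most about 5% (10%), and lower if the measures are positively correlated. Estimating the SD from the 20 patients, or an unequal split at the look, raises these figures.

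Then give the power statement its own basis. If the sponsor intends the look as advisory, for harm only and without any efficacy claim, the plan should say so and state that the final test keeps the 0.05 level. The 0.02% per measure under a 0.56 SD benefit can then be cited for the small loss of power.

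The cost is a few sentences and a less favourable figure. The design does not change.

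A stricter trigger is optional and is the sponsor's choice. A limit of Z ≥ 3 (Haybittle-Peto type) is 3 × 0.447 = 1.34 SD at 10 per arm. It gives 0.13% per measure and about 0.5% over four with known SD, or 0.38% and about 1.5% with the SD estimated on 18 df. It would be less sensitive to moderate harm, so correcting the probabilities alone is sufficient.

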Methadone excretion occurs by demethylation primarily by cytochrome P450 3A4 and is renally removed from the body, yet urine PH and autoinduction may influence its rate of excretion.² Its metabolism is also influenced by previous narcotic used as half-life significantly drops with chronic use of narcotics, and a steady state may take longer to reach in these patients due to autoinduction of CYP3A4. CYP3A4 inducers such as rifampin, rifabutin, carbamazepine, phenytoin, phenobarbital, abacavir, and St. John's Wort will increase methadone metabolism and decrease it concentration in the blood stream, while CYP3A4 inhibitors such as fluconazole, fluvoxamine, fluoxetine, paroxetine, HIV-1 protease inhibitors, erythromycin, ketoconazole, and grapefruit juice will increase serum levels of methadone.²

Methadone use has long been studied and bolstered by its low cost, long half-life, convenient dosing schedule, excellent oral bioavailability, and slow onset to withdrawal.² Despite its positives, methadone, as other narcotics, may be dangerous when abused, yet by minimizing dosing, these risks may be abated.

IV dosing typically ranges from 2.5mg to 10mg every 8-12 hours, with PO forms dosed at 5-20mg every 6-8 hours. Patient with renal failure should be dosed no more frequently than every 6 hours and with more severe disease, no more than 8-12 hours. Cirrhotic patients with liver failure do not need to have their doses altered. Due to the factors listed above, the literature demonstrates up to a 17-fold inter-individual variation in methadone blood concentrations for a given dosage.

In a series of women undergoing caesarean delivery, methadone administration was associated with lower pain scores and 40% lower overall opioid consumption than control subjects undergoing the same procedure who received iv morphine or fentanyl post-operatively. Over sedation of the respiratory system occurred in one of 25 patients in the methadone group and three of 50 in the control sample. The authors comment on the concern for QT interval prolongation with methadone use, but cite that this is reported only with chronic use, not with single operative dose administration.

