The sample size was determined using the Gottschalk study listed in the reference section which used methadone vs. sufentanil in 29 patients undergoing lumbar fusion surgery and the measures for pain level and total narcotic usage at 48 hours to determine an 'n' for the total study population, using a power of 0.80. The details of the calculations is listed in the data analysis section (7a) below and calculated with the suggestion of the statistician on the IRB. The assumptions with which the outcomes are hypothesized are the result of previously published data using similar populations. Two sample t-tests are appropriate to determine statistical significance between mean pain scores between different patients in the control and study groups for each individual time point as there will be no censoring of the study data. Ranked T-test may also be used if outliers are present, however patients with unusual post-operative courses may be excluded if their reason for prolonged hospitalization is unrelated to immediate post-operative pain

control. The large sample size plans to take into account possible outliers that may not be included in final analysis, despite their mention in study write-up to determine why their post-operative hospitalization was prolonged. Additionally, data about patients' mean time to ambulation, mean time to discharge, and mean overall narcotic usage will be measured between the control and study populations. Data analysis will be performed with the assistance of the biostatistician listed as a member of the study team, [name], from the Albert Einstein College of Medicine, Division of Biostatistics. Thus, a sample of 60 completed methadone patients will be evaluated against 60 randomized, standard narcotic regimen controls. The mean data for control patients' pain ratings, narcotic usage, time to ambulation, and time to discharge will be obtained, the statistical deviation of this data will be measured and compared to subject data in all facets.

• Take into account anticipated drop-out or loss-to-follow up rate.

We intend to screen 200 patients to have 60 in each arm ultimately included in the study. Since the intervention is a single intra-operative occurrence, that when completed patients cannot reverse, we do not anticipate any drop-out. A two week follow-up visit is a required standard of care for all post-operative patients, without patient loss to follow-up historically. The study is completed at this point.

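### The adverse-event hold rule sets its limit at more than two patients without event type, denominator or comparator, so on its plain reading it does not mark an excess over normal

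*Combined protocol and SAP*

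**What the plan says.** The rule is in section 7 (Data Analysis), under interim analyses and early stopping: "If the methadone intervention contributes greater than normal adverse events (>2 patients) the study will be held from further recruitment". The consequence follows: "The study medication will not be administered further, no dosing changes will be made, and the IRB will be informed". A decision on further accrual is then taken. Section 2 points to this part of section 7 as the data safety monitoring plan, and this is its only numerical trigger for adverse events.

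The safety outcomes are listed separately in section 2. They "include risks of using any opioid narcotic, which include overdose leading to respiratory depression, dependence and QTc prolongation", and the list goes on to obtunded or lethargic states and altered mental status. The hold rule does not say which of these count, or at what severity.

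The only adverse-event rates in the document are in section 1 (Background/Significance), from a caesarean series: "Over sedation of the respiratory system occurred in one of 25 patients in the methadone group and three of 50 in the control sample".

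On numbers exposed, section 7 states: "We proposed to recruit 60 patients to undergo the new treatment and another 60 as controls". Section 2 gives equal allocation, and section 3 says of attrition that "we do not anticipate any drop-out".

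**The concern.** A limit meant to signal more events than usual needs a usual rate to be measured against. This one is a bare count. The same three patients would be a striking number among the first 10 given methadone and an unremarkable one among 60. At the control rate the protocol itself cites, the expected count in a full methadone arm is already above two.

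Both arms receive opioids during surgery and a morphine PCA afterwards, and section 6 accepts that these risks are shared with the other agents used. A count in one arm cannot separate a methadone excess from events that the controls are having too. A trial with no added harm could be held, with study medication withheld and the IRB asked to decide on accrual. Two people applying the rule in good faith could also reach different answers on the same data. Section 7 reports an error rate for its interim comparison of pain, narcotic use, ambulation and discharge, but none for this rule.

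**Working it through.** **Plan's own figure.** The document gives no false-hold probability to reproduce. The arm size used below is the planned 60. The sample size behind it does reproduce: 0.56 SD, 80% power and two-sided 0.05 give 51 per group, raised to 60.

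**Inputs.**
- Threshold: more than 2, so 3 or more (section 7).
- Methadone patients: n = 60, no attrition (sections 7 and 3).
- Cited rates: 1/25 = 4% with methadone, 3/50 = 6% in controls (section 1).
- Assumed rates, not in the document: 1%, 2% and 3%, to show sensitivity.

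**Reading A: absolute count in the methadone arm.** Expected events are 60 × 0.04 = 2.4 and 60 × 0.06 = 3.6.

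P(X ≥ 3) = 1 − P(0) − P(1) − P(2), with X ~ Binomial(60, p):
- p = 4%: 1 − 0.0864 − 0.2159 − 0.2654 = 0.432
- p = 6%: 1 − 0.0244 − 0.0935 − 0.1761 = 0.706
- pooled 4/75 = 5.3%: 0.627
- assumed 1%, 2%, 3%: 0.022, 0.119, 0.269

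A cumulative count cannot fall, so these are also the chances of ever tripping during accrual.

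The same threshold at smaller exposures:
- n = 10: 0.6% at 4%, 1.9% at 6%
- n = 30: 11.7% at 4%, 26.8% at 6%

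**Precision of the cited rates.** Exact 95% intervals are 0.1-20.4% for 1/25 and 1.3-16.5% for 3/50. Across the first, P(3 or more of 60) runs from under 0.01% to over 99.9%; across the second, from 4% to 99.8%. The cited rates therefore cannot fix the false-hold probability.

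**Reading B: excess over controls.** With equal true rates and 60 per arm, the probability that methadone events minus control events exceed 2:
- after the last patient only (exact): 11.7% at 4%, 16.5% at 6%
- at any time in accrual (simulation), patients entering in pairs: about 17% and 25%
- at any time in accrual (simulation), whole groups of five given one arm, as section 2 describes: about 18% and 27-28%

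A hold acts during accrual, so the ever-tripping figures are the ones to compare with reading A. The ratio runs from 0.43/0.18 ≈ 2.4 to 0.71/0.25 ≈ 2.8. Setting reading A against the last-patient figures would suggest about four-fold, which is not like for like.

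**Reading C: events attributed to methadone.** No probability can be computed, because the document gives neither an attribution rule nor a rate of attributed events.

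**The case against.** The sentence contains more than its parenthesis. It speaks of what methadone contributes and of more than the normal number, which could mean attributed events or an excess over controls. On either reading, ordinary over-sedation need not trip the rule. This stands. A reader might infer that the rule would hold 43-71% of trials in which methadone does no added harm; the documents do not support that, since the range needs both the plain count reading and the cited rates. But the text does not choose a reading, and the choice changes the false-hold chance more than two-fold.

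The rates are also weak. They come from 25 and 50 women having caesarean delivery, whereas this trial enrols spinal fusion patients and excludes sleep apnoea, home oxygen and daily opioid use of 10 mg morphine equivalent or more. The true rate could be lower, and at 1-2% the count rule trips in only 2-12% of trials. This stands as a limit on the size. In the other direction, over-sedation is only one event type, and on the count reading adding the other listed safety outcomes would raise the probability.

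Finally, a low bar for pausing can be deliberate caution, and a false hold costs delay. A reader might infer that tripping ends the trial. It does not: the text describes a hold followed by a decision, and reserves stopping for a death found to be caused by methadone. Caution is a legitimate choice, but the committee should know how often its rule would act with no excess present.

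**Conclusion.** The concern holds as one of definition and calibration. Read plainly, the threshold does not separate an unusual number of events from a usual one: at the protocol's only cited rates a full methadone arm would be expected to have 2.4 to 3.6 events, and a hold would follow with probability 43% or 71%.

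Those percentages rest on 60 exposed patients, independent events, over-sedation as the only counted event, and background rates of 4% or 6%. They illustrate the conflict between the rule and the protocol's own figures; they do not forecast this trial. At assumed rates of 1% to 3% the range is 2% to 27%, and on the excess reading it is about 17-28% at the cited rates. The lack of an event definition, denominator and comparator does not depend on any of these rates. No efficacy analysis depends on the rule.

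**What to change.** Amend the monitoring text in section 7 so that:
- the reference to a normal level, the more-than-two count and the rates cited in section 1 are reconciled;
- the events that count are named, consistently with the safety outcomes in section 2;
- the count is stated to be a methadone-arm count, a count of attributed events (with who attributes them and how) or an excess over controls;
- the monitoring committee receives adverse-event counts by arm, with numbers exposed and an exact confidence interval for the difference;
- the false-hold probability of the adopted rule is reported over a range of background rates, calculated over the whole of accrual.

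The threshold itself is for the committee and the IRB, and none is proposed here.

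The cost is a short amendment and by-arm safety tables. Section 2 already has adverse events recorded and controls monitored after surgery, so no new data collection is needed.
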